Administrative data consist of employment records and medical and pharmaceutical claims data. Employment records are available for all employees across treatment and control worksites (both primary and secondary controls). Medical and pharmaceutical claims data are available through Cigna for BJ's employees who are insured through a Cigna plan. In cross-section, approximately 37 percent of all BJ's employees were insured through Cigna during June 2016 (the midpoint of phase 2). Of note, BJ's as an organization is self-insured (i.e. it bears risk of health care spending of its enrolled members), with Cigna as the administrator of its health plans. We used all administrative data available for the entire study period.

A1. Employment records

BJ's provided us with data from their earnings database, which includes data elements that we use both to define our sample (based on hire and termination dates) and to measure key outcomes, such as absenteeism and performance reviews. Information included:

- **Dates and location of employment actions:** Dates and sites of hire, rehire, termination, transfer, and performance review. These data capture employment history across clubs. A small proportion of employees (4.5%) appeared in more than 1 worksite during the study period. We defined these workers' treatment or control assignment using the randomized assignment of their initial worksite, as the decision to leave (or stay) at a worksite could be endogenous. Most employees have one performance review per calendar year.
- **Demographic characteristics:** Characteristics of the working population include age, sex, and race. These are discussed in greater in the section on Analysis below. Worksite level analyses, as described below, were augmented using 2015 estimates of county-level demographic characteristics from the U.S. Census Bureau matched to the locations of each worksite.
- **Employment characteristics:** Characteristics of an individual's job include type of hired arrangement (full time salaried, full time hourly, and part time hourly) and type of job. The types of jobs were grouped into three categories: sales, non-sales (including laborers and helpers, operatives, and service workers), and other (including administrative support, craft workers, and first/mid-level office professionals).

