- **Hours and earnings:** Each employee's hours (including working hours, vacation, sick time, personal time) and earnings in each pay period. Each observation is at the employee, pay-period, earnings-type level. These data include a handful of negative payments/hours that indicate corrections.

We used these data to study several outcomes:

- **Absenteeism:** We calculated absenteeism as an employee's number of sick plus personal hours, divided by the sum of an employee's number of sick, personal, and worked hours. This gives the ratio of absence relative to how much an employee usually works. Vacation and holiday time are excluded from both the numerator and denominator.
- **Performance review:** Employee performance reviews were coded on a 5-point scale, with 1 representing the best performance rating and 5 the worst. We averaged performance review scores (weighted by the duration of time over which a score held) and created a binary indicator where a score of less than 3 was coded as good performance and 3 and greater as poor performance.
- **Employment tenure:** We calculated each worker's length of tenure at BJ's and how many hours he or she worked (including the nature of those hours, such as regular hours and overtime). We defined tenure as the difference between the hire date and the latest

termination date. If there was no hire date recorded in the data, we used the first appearance in our database. If there was no termination or retirement date in the data, we used the end of the study period.

Table 2 provides a summary of demographic and employment characteristics of the population. The data are presented at the employee level (overall and for analytical subsets) and at the worksite level. **Table 3** provides summary statistics for tenure, performance review, and absenteeism gathered among the control worksites during the treatment period.

A2. Medical and pharmaceutical claims data

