The key identifying assumption is that the only mechanism through which being employed in a treatment worksite affects outcomes is through the availability of the wellness program. There are two threats to this assumption. First, to the extent that covariates were not balanced at baseline and those covariates affect the outcomes of interest, that imbalance could bias our estimates. We control for observed covariates and apply weights to balance covariates between treatment and control. Despite these adjustments, unobserved covariates might still be imbalanced.

Second, to the extent that the wellness program affected hiring or tenure of employees, their presence in the data set may be endogenously determined. We address the issue of endogenous entry by pre-specifying a subsample of those who were already employed at the time the intervention began. We defined this more restrictive “stable employment” subsample as comprising employees who had worked continuously for 13 weeks prior to the wellness program. This comes at a cost of reducing the overall sample size. Our goal in choosing the definition for this subsample was to balance the costs and benefits, as detailed in Appendix 2.

In this stably employed subsample, however, exit from the firm's workforce is still potentially endogenous. We deal with this concern in two ways. First, we will test balance on exit between treatment worksites vs. from control worksites overall and for subgroups. Indeed, tenure and time worked are among our primary outcomes. To the extent that we observe any unbalanced exit, we will perform a bounding exercise (assuming that those who exited have outcomes working against any observed effects of the intervention).

D. Subgroup analyses

We pre-specified three subgroup analyses. We selected these subgroups based on differences in key outcomes within the control group for those with different baseline characteristics, such as differences in medical spending by age or in reported exercise by sex (**Table 11**).

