Full-time salary	4.7	7.0	21.3	11.6	12.1	21.7	11.5	11.4	21.8
Full-time hourly	37.4	44.3	66.6	38.6	52.4	66.8	49.0	53.6	66.4
Part-time hourly	57.9	48.7	12.1	49.8	35.5	11.4	39.5	35.0	11.8
Worker Type (%)									
Sales worker	43.2	45.3	23.2	38.4	39.0	22.3	36.2	39.3	23.3
Non-sales worker	45.9	41.8	52.4	46.4	42.8	52.8	47.4	43.7	51.6
Other worker	10.9	13.0	24.4	15.3	18.2	25.0	16.5	16.9	25.0

Notes: Table lists demographic characteristics for the sample covered by Cigna weighted by months of Cigna coverage. About a third of the total sample has Cigna coverage. Age is defined as age at the mid-point of the treatment period (June 2016). This is different from the balance table where age is defined as of December, 2014 (pre-treatment). Thus the means of age in this table are larger than those in the balance table across all samples.

Table 3: Impact on Employment

	Employee-level			Stably Employed Subsample			Worksite-level		
	Mean Value in Control Group (1)	Reduced Form (Linear) (2)	2SLS (Linear) (3)	Mean Value in Control Group (1)	Reduced Form (Linear) (2)	2SLS (Linear) (3)	Mean Value in Control Group (1)	Reduced Form (Linear) (2)	2SLS (Linear) (3)
Absenteeism (%)	2.23 (2.30) 41,376			3.39 (1.97) 13,000			2.90 (0.35) 135		
Performance Review (% ≤ 3)	46.59 (49.88) 27,150			63.64 (48.11) 12,916			65.94 (12.41) 135		
Tenure [§]	416.69 (399.87) 41,376			786.57 (376.96) 13,000			76.08 (4.35) 135		

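### The performance-review indicator cuts an average at 3, so its value depends on how many reviews were averaged; the mean score should be analysed, and the two stated cut-points reconciled

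*Combined protocol and SAP*

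**What the plan says.** Section IV.A1 defines the scale: "Employee performance reviews were coded on a 5-point scale, with 1 representing the best performance rating and 5 the worst". It then reduces each person's reviews in two steps. First, "We averaged performance review scores (weighted by the duration of time over which a score held"; second, it "created a binary indicator where a score of less than 3 was coded as good performance and 3 and greater as poor performance". On frequency it says: "Most employees have one performance review per calendar year". Section V.A takes into the main sample anyone who worked at the company for any length of time in the 36 months.

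Table 3 labels the same outcome "Performance Review (% ≤ 3", which puts an average of exactly 3 on the other side of the cut. Its control entries are "46.59 (49.88) 27,150" for all employees and "63.64 (48.11) 12,916" for the stably employed.

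Section VI.C treats stay as something the program may affect: "Indeed, tenure and time worked are among our primary outcomes". Base equation (1) includes TIME_WORKED and its interaction with treatment. Worksite equation (6) and phase 1 equation (7) do not. In the LATE, TIME_WORKED appears in the first stage (4) but not in the outcome equation (3). Section VI.F offers one functional-form check for binary outcomes: a logit on the same indicator.

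**The concern.** A single rating of 3 is coded poor. Ratings of 3, 3 and 2 average 2.67 and are coded good. Averaging pulls people off the value 3, and because the cut sits at 3, the share below it moves with the number of ratings even if every rating comes from the same distribution. The expected mean score does not move in this way.

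The number of ratings follows time employed, which is determined after randomization. If the program changed retention, the good-performance row could shift with no change in how anyone was rated. The planned logit would inherit the problem.

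**Working it through.** **1. Reproducing Table 3.** For a 0/1 variable, SD = 100·√[p(1−p)]. With p = 0.4659 this gives 49.88 (stated 49.88); with p = 0.6364 it gives 48.10 (stated 48.11). The entries behave as a binary indicator. The check cannot show which side of the cut an exact 3 fell on.

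**2. Dependence on the number of reviews, by hand.** Assume ratings 1–5 have shares 5/30/45/15/5% and reviews are independent and equally weighted.
- One review: P(<3) = 5 + 30 = 35%.
- Two reviews: P(sum ≤ 5) = 0.0025 + 0.03 + 0.135 + 0.285 = 45%.
- Under the Table 3 label: P(≤3) is 80% with one review. With two, it is 0.4525 + 0.2975 = 75%. The direction reverses.

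**3. Wider range, by simulation.** The documents give neither the rating distribution nor the within-person correlation. Assumed: five-level ratings from a latent normal, 46.6% below 3 at one review, 5–25% at 4–5, correlation 0–0.97.

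| Reviews averaged | P(mean < 3) | Mean score |
|---|---|---|
| 1 | 46.6% | reference |
| 2 | about 50–67% | unchanged |
| 3 | about 52–78% | unchanged |

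Each person's share of ratings below 3 is also unchanged. The step shrinks towards zero as a person's ratings become constant: at correlation 0.999 in the 46.6% scenario, one to two reviews moves P(good) only from 46.6% to 47.3%. The 46.6% anchor is an assumption too, since Table 3's 46.59% is already a mixture over one or more reviews.

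**4. Size in the arm contrast.** Suppose the program moved 10% of staff from one review to two. With 10–15% of ratings at 4–5 and correlation up to 0.6, P(good) with two reviews is 58–63%, a step of about 11–16 points. The shift is 0.10 × 11–16 ≈ 1.1–1.6 points. Over the full range in step 3 it is 0.10 × 3.4–20.4 ≈ 0.3–2.0 points.

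Table 3 gives a worksite-level SD of 12.41 over 135 control sites.
- 25 treated sites: SE = 12.41·√(1/25 + 1/135) = 2.70 points.
- 20 treated sites, the base worksite specification: SE = 12.41·√(1/20 + 1/135) = 2.97 points.

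So 1.1–1.6 points is about 0.4–0.6 of the 2.70 SE, before covariate adjustment.

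**5. Which models are exposed.**
- Equations (6) and (7): nothing adjusts for stay.
- Equation (1): the adjustment is partial. It is linear and uses share of hours, whereas reviews accrue by calendar year. A part-timer present for three years has few hours but about three reviews.
- LATE: fitted participation is near zero in controls (Table 10) and can rise with TIME_WORKED in the treated. Equation (3) does not hold TIME_WORKED fixed, so an indicator that rises with stay loads on γ₁ with no program effect on ratings or stay. An illustrative simulation with ratings unrelated to stay gave about 2 points per completed module for the indicator and about 0 for the mean score. The 2 depends on the assumed link between hours and reviews.

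**6. The gradient in Table 3.** Good reviews are 46.59% in all controls (mean tenure 417 days) and 63.64% in the stably employed (787 days). By subtraction, the other 14,234 reviewed controls are at (27,150 × 46.59 − 12,916 × 63.64)/14,234 = 31.1%, approximate because balance weights differ.

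**7. Precision.** If employees were independent and the score normal, the cut would keep φ(z)²/[p(1−p)] of the information: 0.635 at p = 0.466 and 0.609 at p = 0.636. Employees are clustered. Assuming the treatment arm has the controls' review rate, 7,288 × 27,150/41,376 = 4,782 treated are reviewed. The independent-data SE is then 100·√[0.4659 × 0.5341 × (1/4,782 + 1/27,150)] = 0.78, and the design effect is (2.70/0.78)² ≈ 12.

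Let n be the effective number of reviewed staff per site and 100φ = 39.75, so (100φ)² ≈ 1,580. Between-site variance on the latent scale is τ² = [12.41² − 2,488/n]/1,580. Efficiency is [τ² + (1−τ²)/n] ÷ [12.41²/1,580].
- n = 201 (27,150/135): 0.0942/0.0975 ≈ 0.97.
- n = 80 (assumed, allowing for hours weighting): 0.0893/0.0975 ≈ 0.92.

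**The case against.** The strongest reply is that bias in the arm contrast needs a program effect on stay, which nobody knows. Tenure is reported in the same table, balance on exit is to be tested, and a bounding exercise follows if exit is unbalanced. Equation (1) also conditions on TIME_WORKED. All of that stands, and it keeps the likely bias small. It does not remove the defect: the bounding concerns people who exited, not the different number of ratings behind each remaining value, and equations (3), (6) and (7) lack the adjustment.

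Three stronger readings are tempting and should be resisted.
- *Dichotomizing wastes a quarter or more of the information.* That holds for independent employees with a near-normal score. The rating distribution is not given, and even with independent data the loss for single reviews confined to 2 and 3 could be zero. With the between-site spread in Table 3, the indicator keeps about 92–97% of the efficiency under a normal score. Covariate adjustment could reduce the between-site variance and change this, but the documents do not support a large power loss.
- *Table 3 demonstrates the artefact.* The 46.59% to 63.64% gradient fits it, and equally fits better performers staying longer.
- *Longer stay by itself biases the treatment effect.* For the arm contrast it does so only if stay differs by arm. The LATE as printed is the exception.

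It is also fair to say that the mean score is no complete cure: its expectation is free of tenure only if ratings do not drift with tenure and exit is unrelated to rating.

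**Conclusion.** The point holds in limited form. As defined, the indicator mixes performance with the number of reviews averaged, unless each person's ratings barely vary. The direction depends on an unresolved conflict: below 3 in Section IV.A1, ≤ 3 in Table 3. With the Section IV.A1 rule and ratings averaging under 3, more reviews mean more people coded good; with ≤ 3 the effect generally runs the other way or is flat.

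The probable distortion of the arm contrast is modest, roughly half a worksite-level standard error, and conditional on an assumed 10% of staff gaining a second review. The LATE needs no such condition and is the more serious exposure. The rating distribution, the within-person correlation and the 46.6% anchor are all assumptions, so the ranges indicate scale and are not estimates for this trial. This is a worthwhile, inexpensive correction, not a threat to the trial's main conclusions.

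**What to change.** In Section IV.A1 and the Table 3 row:
- Analyse the duration-weighted mean score (1–5) in equations (1), (6), (7) and the LATE. If a percentage is preferred, use each employee's share of reviewed time with a rating below 3.
- Keep the cut of the average as a sensitivity analysis.
- State one cut-point and use it in both the text and the table label.
- Report the number of reviews per person by arm, so that readers can judge whether stay could have moved the row.

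The cost is a sentence or two, a relabelled row and one descriptive line; no new data are needed, since the plan already computes the average. The effect would be in rating points and less directly comparable with the binary version, which the sensitivity analysis covers. Selection through exit related to rating would remain. So would any loading in equation (3) from ratings that truly vary with hours worked, because TIME_WORKED is absent there; the write-up should say so.

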Notes: Table reports the coefficient on TREATMENT from estimating equation (1) by OLS (column 2), and the coefficient on PARTICIPATION from estimating equation (2) by IV (column 3). Standard errors are listed in parentheses. Column 1 reports the mean of each employment outcome in the control group for each sample (with standard deviation in parentheses, followed by the number of observations for each outcome). All regressions will include demographic and employment controls (age, sex, age-sex interactions, race/ethnicity, Cigna coverage status, full-time status, paid hourly status, and job category) and cluster standard errors at the worksite (for employee-level regressions). Employee-level and stably employed subsample control means are weighted by a weight that balances treatment and control on demographic characteristics. Worksite-level control means are not traditionally weighted: individual-level records are collapsed at the worksite-level and weighted by the total number of hours worked at each worksite. For worksite level results on tenure, the outcome was defined as the percent of total days at the worksite during the study period that was worked by employees at the worksite.

§ Tenure was defined as the number of days worked during the treatment period for the employee-level mean and stably employed subsample mean; it was defined as the percent of the entire treatment period worked by employees in the worksite-level mean.

Table 4: Impact on Medical & Pharmaceutical Spending and Utilization

	Employee-level			Stably Employed Subsample			Worksite-level (per 2000 work hours)		
	Mean in Control Group (1)	Reduced Form (Linear) (2)	2SLS (Linear) (3)	Mean in Control Group (1)	Reduced Form (Linear) (2)	2SLS (Linear) (3)	Mean in Control Group (1)	Reduced Form (Linear) (2)	2SLS (Linear) (3)
Medical Spending									
Total Spending	4800.57 (18559.82)			4721.85 (19056.92)			5044.74 (2994.54)		
Medical Utilization									
Number of Office visits	3.90 (4.47)			3.95 (4.33)			4.21 (0.93)		
Number of Hospitalizations	0.09 (0.40)			0.08 (0.36)			0.08 (0.05)		
Number of ER Visits	0.28 (0.75)			0.26 (0.61)			0.27 (0.11)		
Pharmaceutical Spending									
Total Spending	1237.60 (6921.32)			1227.32 (7115.67)			1317.72 (1145.17)		
Pharmaceutical Utilization									
Number of Distinct Medications	5.49 (6.44)			5.91 (6.54)			6.00 (1.30)		
Total Medication Months	11.20 (19.31)			11.41 (19.37)			12.39 (4.38)		
N	7,174			5,779			135		

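### Tenure, named among the primary outcomes, has two incompatible employee-level definitions: the text counts service from the hire date, Table 3 counts only days in the treatment period

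*Combined protocol and SAP*

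**What the plan says.** Section IV.A1 (Employment records, Employment tenure): "We defined tenure as the difference between the hire date and the latest" termination date. Two rules for missing dates follow: "If there was no hire date recorded in the data, we used the first appearance in our database", and "If there was no termination or retirement date in the data, we used the end of the study period". The end of the spell is therefore bounded and the start is not. The same section lists rehire dates among the data received, but does not say which hire date is used or whether gaps between spells are removed.

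Table 3, footnote: "Tenure was defined as the number of days worked during the treatment period for the employee-level mean and stably employed subsample mean"; at worksite level, "it was defined as the percent of the entire treatment period worked by employees in the worksite-level mean".

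Section VI.C (Addressing endogeneity concerns), directly after announcing a test of balance on exit: "Indeed, tenure and time worked are among our primary outcomes".

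**The concern.** The two employee-level definitions are different outcomes. Someone hired on 1 January 2005 and still employed at the end of 2017 has about 13 years of tenure under the text and 1,096 days under Table 3. Only the part from January 2015 onward can respond to the program.

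The plan sets out to fix its analysis before the arms are compared. With two definitions of a primary outcome, the choice is still open. If the text rule reached the regression, variation in past service would be added to the outcome and a real effect on retention would be harder to see. The stably employed subsample is the most exposed: its members all worked through the 13 weeks before the program, so all have service before 2015.

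**Working it through.** **Inputs**
- Treatment period (Section VI, opening): January 2015 through December 2017, so 365 + 366 + 365 = 1,096 days.
- Table 3 control means (SD): all employees 416.69 (399.87), n = 41,376; stably employed 786.57 (376.96), n = 13,000.
- Appendix 2, controls employed for the 13 weeks before 1 March 2015 (about 13,500): about 75% still employed on 1 December 2015 and 51% at the end of December 2017.
- Appendix 2: about 7,900 controls employed on 1 January 2014 were still working on 1 January 2015.

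**1. Which rule produced Table 3?** Mean in-window tenure is the area under the retention curve over the window. Take 100% for the 59 days to 1 March 2015, then 275 days to 1 December 2015, then 762 days to the end of 2017.
- Linear decline: 59 + 275 × (1 + 0.75)/2 + 762 × (0.75 + 0.51)/2 = 59 + 240.6 + 480.1 = 779.7 days, 0.9% below 786.57.
- Exponential decline: 59 + 275 × 0.25/ln(1/0.75) + 762 × 0.24/ln(0.75/0.51) = 59 + 239.0 + 474.2 = 772.2 days, 1.8% below.
- Cruder versions that use only the 51% point give 797.6 to 841.9 days (1.4% to 7.0% above).

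Both means also fit inside the window: 416.69/1,096 = 38.0% and 786.57/1,096 = 71.8%. The SD of 376.96 is below the maximum possible for a variable bounded by 0 and 1,096 with that mean, √(786.57 × 309.43) = 493. Table 3 is in-window.

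**2. What would the text rule give?** The 7,900 carry at least 365 days of service before 2015. Assume that they belong to the stably employed sample, and ignore the balance weights.
- Stably employed: 7,900 × 365/13,500 = 214 to 7,900 × 365/13,000 = 222 extra days. The remaining members worked at least December 2014 (31 days), which raises the addition to 226–234 days. The mean becomes at least about 1,013–1,021 days.
- All controls: 7,900 × 365/41,376 = 70 extra days, so a mean of at least about 486.

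These are lower bounds, because hire dates before 2014 are not given. On this assumption the text rule cannot yield 786.57.

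**3. What does Table 3 count?** A five-day week over the window has about 1,096 × 5/7 = 783 working days. A mean of 786.57 exceeds that, and step 1 matches it in calendar days. The footnote's days worked must therefore be calendar days employed.

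**4. Possible loss of precision.** The documents give no SD for pre-trial tenure. If it is independent of in-window tenure (assumption), the combined SD is √(376.96² + s²):

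| Assumed s | Combined SD (days) | Multiple of 376.96 |
|---|---|---|
| 1 year (365.25 days) | 525 | 1.39 |
| 3 years | 1,159 | 3.07 |
| 5 years | 1,865 | 4.95 |

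These are unadjusted SDs. They ignore clustering and covariates, so they are not ratios of the model's standard errors.

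**The case against.** The strongest reply is that the two places can be read in sequence: Section IV.A1 sets the ends of the spell and handles missing dates, and Table 3 cuts the spell to the window. Section IV.A1 itself describes the Table 3 statistics as covering the treatment period, and the worksite version is already in-window. Nothing shows that the uncut rule has been or will be used in a regression. This supports the in-window version as the intended one and keeps the point modest. It does not remove it: the only definition in the outcomes section still has no start date, and a pointer to a table does not amend it.

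A reader might infer more than the documents support, in four ways.
- *That the definition could hide unbalanced exit.* Section VI.C mentions tenure beside the exit test but does not say that the test uses this variable. Exit turns on termination dates, and Appendix 2 measures retention as the share still employed on a date.
- *That treatment cannot affect any rehire gap the text rule counts.* Only gaps before 2015 are out of reach; leaving and returning within the window could respond to the program. That gaps are counted at all is inferred from the use of the latest termination date.
- *That standard errors would grow by a known large factor.* The factor depends on an SD that is not given, and the age and job covariates in Section VI.A would plausibly absorb part of the extra variation.
- *That the estimate would be biased.* Under randomization, pre-trial service mainly adds noise and chance imbalance.

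**Conclusion.** The inconsistency stands. A variable named among the primary outcomes has two employee-level definitions that disagree for everyone hired before 2015. That covers all of the stably employed but apparently only a minority of the 41,376 controls in the full sample, of whom 13,000 are stably employed. The plan's own figures identify the in-window rule as the one used in Table 3, so Section IV.A1 is the text to correct.

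Followed literally, that section would raise the stably employed control mean from 786.57 to at least about 1,013–1,021 days, on the membership assumption in step 2. The cost in precision cannot be fixed from the documents; an inflation of the unadjusted SD by 1.4 to 5 times is an illustration for assumed SDs of 1 to 5 years and independence. The point should be settled before the arms are compared, but it does not show that any planned result is wrong.

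**What to change.** In Section IV.A1, define employee-level tenure as calendar days employed from the later of the hire date and 1 January 2015 to the earlier of the termination date and 31 December 2017. State which hire date applies to rehired workers and how gaps between termination and rehire inside the window are counted; this is a choice to be made, since neither passage settles it. In the Table 3 footnote, replace days worked with days employed. Confirm that the regression code, and any exit check based on tenure, use this version. The worksite measure is already in-window and needs no change. The cost is a few sentences of SAP wording and a code check; no new data are needed.
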